Study Title: Persistence of Glaucoma Patients With Web-Browser-Based Visual Field Test

Principal Investigator: [name]

NCT Number: NCT05690152

Unique Protocol ID: 202207403

IRB ID: 202207403

Date: 9/5/2025

Web Browser Visual Field Study

PI: [name]
IRB ID #: 202207403

Project Details

I. Project Introduction

I.1

Project to be reviewed by:
IRB-01

I.2

Project Title:
Visual Field Telemedicine in Glaucoma Patients using a Web Browser-Based Test Strategy

I.3

Short Title (optional):
Web Browser Visual Field Study

I.4

Provide a short summary of the purpose and procedures of the study proposed in this IRB application.

- DO NOT include information on studies not proposed in this application.***
- Use LAY terminology only. This must be easily understandable by IRB community members and nonscientists.***
- DO NOT cut and paste technical abstracts from funding applications that may not be understood by a general audience.***

The purpose of this prospective study is to determine the reliability of and patient compliance with a testing strategy with a novel home, web-based visual field test, EyeSimplify (M&S Technologies, Niles, IL), for purposes of surveilling glaucomatous progression. In this study, EyeSimplify will be compared to the current accepted gold standard Standard Automated Perimeter, the Humphrey Visual Field Analyzer (Carl Zeiss Meditec Inc., Dublin, CA).

The proposed study will be conducted at the University of Iowa Hospitals and Clinics and via telemedicine encounters. We estimate 50 subjects will be recruited to participate in the study. Data collected will not include patient identifiers.

Research involves retrospective collection of data, documents, and records, as well as prospective collection of visual field testing performance. The source of data will be retrospective review of computerized or written medical record and testing conducted in clinic beginning upon IRB approval. Patients with suspected, mild, moderate, or severe glaucoma will be included. Clinical data including age, gender, ethnicity, visual acuity, intraocular pressure, severity of disease, Humphry Visual Field performance, EyeSimplify Visual Field performance, and satisfaction survey will be recorded.

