Following study recruitment, subjects will be asked to take EyeSimplify visual field tests at home biweekly for six months. They will have no additional responsibilities between tests. Subjects will access the EyeSimplify web browser on their personal electronic devices using a link and login credentials provided to them by a research assistant. Upon logging into the EyeSimplify web browser, subjects will click the "Start Test" button found along the left side of the window and follow the prompts presented on screen to calibrate their screen. Screen calibration involves holding a driver's license/credit card/ID to the screen to ensure the test window is the appropriate dimensions. Following screen calibration, subjects will follow the test prompts presented on screen to complete their visual field test. Test results are automatically sent to the research assistant who issued the exam, so subjects may exit the browser after each test. Upon study completion, subjects will be asked to fill out a brief satisfaction survey.

M&S Technologies is the developer of the EyeSimplify web-based visual field test. [name], [name], and [name] have no financial or intellectual relationship with M&S Technologies, aside from the current study and an additional study under IRB review investigating the Pico Virtual Reality Headset visual field test.

As the developers of the web-based visual field test, M&S Technologies maintains a secure, encrypted, HIPAA-compliant database of EyeSimplify users. This database includes patient profiles containing unique patient IDs (de-identified), birth year, and visual field testing results. Outside of this testing information, M&S Technologies does not have access to any additional patient information.

I.5

Specify your research question(s), study aims or hypotheses (do not indicate "see protocol")
Aim 1: Determine test reliability of the EyeSimplify (M&S Technologies, Niles, IL) home, web-based visual field test in glaucoma patients.
Aim 2: Determine the concordance of EyeSimplify to the Humphrey Visual Field Analyzer (Carl Zeiss Meditec Inc., Dublin, CA) in identifying visual field loss progression.
Aim 3: Determine patient compliance with and tolerance of biweekly EyeSimplify testing for a 6 month period, assessed by test recordkeeping and a patient experience survey.

Primary Hypothesis: The EyeSimplify visual field test will produce reliable visual field testing data.

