- VII.B.23** *Describe in detail procedures in place to limit access to authorized study personnel for the storage, control, and dispensing of the investigational devices. (For example, investigational devices are kept in a locked area away from approved devices or have a keyed interlock, and only study personnel authorized to dispense the device have the keys)*
EyeSimplify is a web-based visual field testing platform. Access requires subject-specific login credentials (created by a research assistant upon study recruitment) and to be granted tests (subjects will be unable to take an EyeSimplify visual field test if they do not have a test sent to them by a research team member, even if they have login credentials).
- VII.B.24** *Is the device FDA-approved for the way it will be used in this study?*
No
- VII.B.25** *Is there an IDE (Investigational Device Exemption) for this device in this research project?*
No
- VII.B.29** *Indicate the appropriate FDA status you and/or the sponsor are requesting for the use of this device in this study.*
Non-Significant Risk (NSR) device/software
- VII.B.31** *Provide a detailed rationale for why this device meets the FDA definition of a Non-Significant Risk Device (NSR)*
Per M&S, the EyeSimplify web browser-based visual field is "Class I" and doesn't need FDA Approval (highest-risk like neurostimulators) or FDA Clearance (medium-risk devices / 510(k)). They include it in their device listings on the FDA Establishment Registration (screen prints attached to additional documents section).
- Under 21 CFR 812.3(m), a "serious risk" device means an investigational device that:
1. Is intended as an implant and presents a potential for serious risk to the health, safety, or welfare of a subject;
 2. Is purported or represented to be for use supporting or sustaining human life and presents a potential for serious risk to the health, safety, or welfare of a subject;
 3. Is for a use of substantial importance in diagnosing, curing, mitigating, or treating disease, or otherwise preventing impairment of human health and presents a potential for serious risk to the health, safety, or welfare of a subject; or
 4. Otherwise presents a potential for serious risk to the health, safety, or welfare of a subject.
- The EyeSimplify web browser-based visual field test does not meet any of these criteria, qualifying it as a nonsignificant risk medical device.
- VII.B.32** *Provide a summary of prior investigations with this device.*

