If a subject fails to complete a scheduled home visual field test, the PI or research assistant will reach out to the patient via email and/or telephone to determine the cause of the missed test. If the patient can be contacted and wishes to continue participating in the study, the PI or research assistant will prompt the subject to complete the exam. If a patient misses a second scheduled test, the patient will be considered lost to follow-up and will not be contacted again.
- VII.E.9** *Will subjects be provided any compensation for participating in this study?*
No

VIII. Risks

- VIII.1** *What are the risks to subjects including*
- *emotional or psychological*
- *financial*
- *legal or social*
- *physical?*
Loss of time and confidentiality
- VIII.2** *What have you done to minimize the risks?*
- *If applicable to this study ALSO include:*
 - *How you (members of your research team at Iowa) will monitor the safety of individual subjects.*
 - *Include a description of the availability of medical or psychological resources that subjects might require as a consequence of participating in this research and how referral will occur if necessary (e.g. availability of emergency medical care, psychological counseling, etc.)*

Patient privacy will be protected by separating patient identifiers from the data and storing the data on a password-protected computer in a locked office within the Ophthalmology Department. To prevent a loss of confidentiality from occurring, all data will be located on a UIHC encrypted, password-protected Department of Ophthalmology server. Only designated research team members and PI will have access to the drive. Any paper documents will be kept in a locked file cabinet in the principal investigator's office.

All data collected by M&S Technologies will be stored in a secure, encrypted, HIPAA-compliant database. De-identified subject data is ultimately aggregated for quality improvement purposes by M&S Technologies.

The study utilizes data generated as a consequence of routine clinical practice, as well as additional home, web-based visual field tests. The study poses no therapeutic questions and no interventions; no treatment is directed by the study. Therefore, the study poses no substantive risk to the patient other than loss of time and confidentiality. It does not impose any significant burden on the patient.

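### The lost-to-follow-up rule is triggered by the compliance outcome itself, so behaviour after a second missed test probably goes unobserved and six-month compliance (Aim 3) depends on an undefined denominator

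*Combined protocol and SAP*

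**What the plan says.** Aim 3 (I.5) is to "Determine patient compliance with and tolerance of biweekly EyeSimplify testing for a 6 month period". The same aim names its data sources, with compliance and tolerance to be "assessed by test recordkeeping and a patient experience survey". The cover title also puts the behaviour at the centre: "Persistence of Glaucoma Patients With Web-Browser-Based Visual Field Test". On the schedule, I.4 states that "subjects will be asked to take EyeSimplify visual field tests at home biweekly for six months"; the number of tests is not given.

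Under VII.E.8, a first missed test leads to contact by email or telephone. If the subject wishes to continue, "the PI or research assistant will prompt the subject to complete the exam". For the next miss the rule is: "If a patient misses a second scheduled test, the patient will be considered lost to follow-up and will not be contacted again". The section does not say whether the two misses must be consecutive, or whether a late test taken after a prompt still counts as missed.

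Section VII.B.23 describes access to the test: "subjects will be unable to take an EyeSimplify visual field test if they do not have a test sent to them by a research team". VII.B.21 adds that the browser logs completed tests automatically. On the survey, I.4 says: "Upon study completion, subjects will be asked to fill out a brief satisfaction survey". The data analysis section (XI.1) plans a Bland-Altman comparison of progression trends. It gives no compliance formula, denominator, analysis set or rule for missing tests.

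**The concern.** A missed test is non-compliance. It is the event that Aim 3 exists to count, and it differs from a subject who can no longer be observed. The plan treats the second such event as the end of follow-up. If no further tests are sent, intermittent use cannot be told apart from stopping, because nothing is seen after the second miss. Where the misses are cumulative, a subject on course to complete 11 of 13 tests gets the same status as one who abandons testing in the first month.

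At stake is whether the study can report six-month compliance at all. Those still under follow-up at the end are selected for having missed few tests, so their compliance looks high whatever the true rate. Two further effects follow. Prompting after the first miss mixes assisted with unassisted completion. A survey given at study completion may reach mainly the good adherers, so tolerance would be judged by the people who tolerated the testing.

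**Working it through.** The documents state no compliance figure, so there is nothing to reproduce. The check asks how far the reported result could move under the rule.

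**Inputs from the documents.** Biweekly testing for six months (I.4); loss at the second missed test (VII.E.8); 50 subjects (VI.1).

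**Assumptions.** n = 13 tests (26 weeks / 2; 12 to 14 also tried). Per-test completion p of 0.95, 0.90 and 0.80, independent between tests. Misses are cumulative. A late prompted test still counts as missed. No tests are taken after loss.

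**Formulas.**
- No miss: P0 = p^13. One miss: P1 = 13(1−p)p^12. Lost: 1 − P0 − P1.
- Compliance among those retained: (P0 + P1 × 12/13) / (P0 + P1).
- All enrolled, later tests counted as missed: p × E[S] / 13, where S is the number of tests scheduled up to and including the second miss, or 13 if there is none.

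**Example, p = 0.90.** P0 = 0.254 and P1 = 0.367, so 1 − 0.254 − 0.367 = 0.379 are lost, about 19 of 50. Retained: (0.254 + 0.367 × 12/13) / 0.621 = 0.955. E[S] = 11.245, so all enrolled: 0.90 × 11.245 / 13 = 0.778.

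| True completion | Lost | Of 50 | Retained only | Later tests = missed |
|---|---|---|---|---|
| 95% | 13.5% | 7 | 96.9% | 90.9% |
| 90% | 37.9% | 19 | 95.5% | 77.8% |
| 80% | 76.6% | 38 | 94.1% | 52.7% |

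True completion falls by 15 points, yet the retained-only figure falls by less than 3. At a true 80%, the same behaviour can be reported as 94% or 53%.

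**Number of tests.** At p = 0.90, 12 tests give 34.1% lost and 14 give 41.5%. The lowest compliance possible for a retained subject is 11/12 = 91.7%, 12/13 = 92.3% or 13/14 = 92.9%.

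**A third denominator.** Tests completed over tests scheduled up to loss returns 95%, 90% and 80% in the three rows above, because p is constant. It does not do so otherwise. By simulation with a true average of 80% over 13 tests:
- linear decline from 95% to 65%: reads 82.7%;
- subject-level completion drawn from Beta(4,1): reads about 85.3%;
- half of subjects at 95% and half at 65%: reads 85.7%.

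The bias is upward because poor adherers and late months contribute fewer scheduled tests.

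**Consecutive reading.** If the two misses must be consecutive, about 11% are lost at p = 0.90 and those retained average 91.5%. A retained subject could then complete as few as 6 of 13 tests (46%).

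**The case against.** The strongest reply is that VII.E.8 answers a form question about recontact. It says that contact ends. It does not say that tests stop being issued, that the subject is withdrawn or that data are excluded. The browser log would still give each subject's record up to the second miss, and time to the second miss is observable for everyone. Tests completed over tests scheduled up to loss is unbiased when completion is constant. A late second miss costs few tests: at 90% completion the average is 13 − 11.245, or about 1.8 scheduled tests per enrolled subject. The completion rates used above are not in the documents, and the prompt may rescue a first miss.

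Much of this stands. A reader might infer that good adherers are removed and that those who remain must show at least 92% compliance by construction. The documents do not support that as a fact. It needs about 13 tests, cumulative misses, late prompted tests counted as missed and a retained-only denominator, and none of these is stated. Removal is itself an inference.

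The reply does not dispose of the point. A subject who is classed as lost and never contacted again cannot be assumed to keep receiving tests, and without a test sent by staff the subject cannot test. The up-to-loss denominator works only under constant completion, which is hard to presume in a study of persistence.

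**Conclusion.** The concern holds in a conditional form. The plan makes the Aim 3 outcome the trigger for loss to follow-up, nothing elsewhere in the documents repairs this, and behaviour after the second miss is probably not observed. Under the stated assumptions, between 13.5% and 77% of subjects are classed as lost as true completion runs from 95% to 80%. Retained-only compliance stays between 94% and 97%. Redefining the denominator alone does not cure this, since a true 80% can still read about 83% to 86%.

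The size rests on the cumulative reading, which is the plainer one because the text does not ask for consecutive misses, and on how late prompted tests are counted. It would be too strong to say that the trial cannot report compliance at all: compliance up to the second miss remains available for every enrolled subject.

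**What to change.** In VII.E.8, keep issuing every scheduled test to every enrolled subject for the full six months unless consent is withdrawn. If staff time must be limited, cap the calls and not the tests. Offer the end-of-study survey to all enrolled subjects.

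In XI.1, state the number of scheduled tests and define compliance as tests completed divided by tests scheduled, in all enrolled subjects. Log each prompt, and report tests completed late after a prompt separately.

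The cost is some extra staff work in sending links to non-responders and keeping the prompt log; completion is already recorded automatically.

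The IRB letter in the same document records closure on 09/05/25, so conduct may no longer be open to change. In that case, report compliance for all enrolled subjects with later tests counted as missed and with tests scheduled up to loss, beside the retained-only figure. State the two-miss rule and how it was applied, including whether tests continued to be sent. Do not present the retained-only figure as six-month compliance.

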Secondary Hypothesis: The EyeSimplify visual field test will be non-inferior to the Humphrey Visual Field Analyzer in identifying glaucomatous progression trends.

I.6

Background and significance and/or Preliminary studies related to this project. (do not indicate "see protocol")
Glaucoma is the leading cause of irreversible blindness worldwide (1-2). Standard Automated Perimetry is the current accepted standard for diagnosis and monitoring of glaucomatous visual field loss (3), and the Humphrey Visual Field Analyzer (HFA; Carl Zeiss Meditec Inc., Dublin, CA) is the automated perimeter that is most frequently used due to it currently having the largest market share. The HFA is a useful clinical tool; however, it is a large, expensive device. Testing takes approximately seven minutes per eye when using the Swedish Interactive Threshold Algorithm (SITA) Standard testing algorithm, and testing is typically only done at 6-12 month intervals. Recently, there has been interest in the development of alternative methods to monitor visual field progression outside of the clinic setting (4). EyeSimplify (M&S Technologies, Niles, IL) is a web-based visual field test that aims to increase the frequency at which patients can test their visual fields, improve accessibility to visual field testing, and potentially identify visual field loss progression more quickly.

I.7

Literature cited / references (if attaching a grant or protocol enter N/A).
1. Quigley HA. Number of people with glaucoma worldwide. Br J Ophthalmol. May 1996;80(5):389-93. doi:10.1136/bjo.80.5.389

doi:10.1136/bjo.2005.081224

II. Research Team

II.1

Principal Investigator

Name	E-mail	College
[name]	[contact]	Carver College of Medicine

II.2

Team Members

UI Team Members

Name	E-mail	College	Contact	Key Prsn	UI COI	VAMC COI	Consent Process Involvement	Deactivated
[name]	[contact]	Carver College of Medicine	Yes	Yes	No		Yes	No

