- Describe study populations separately if they will be participating in different procedures - include CONTROL population if applicable.*
- DESCRIBE:**
- *What subjects will be asked to do/what happens in the study (in sequential order)*
 - *The time period over which procedures will occur*
 - *The time commitment for the subject for individual visits/procedures*
 - *Long-term followup and how it occurs*
- Potential subjects will be approached at the time of their regularly scheduled appointment to participate in this research study. The research assistant will answer any questions potential subjects may have regarding the purpose, procedure, and risks of the study. If they agree to participate, subjects will sign an informed consent.
- In addition to routinely scheduled clinical examination, including visual field testing (VF) with the Humphrey Field Analyzer (HFA), subjects will be asked to complete biweekly VF for six months using EyeSimplify, a novel, web-based VF, at home. Subjects will be instructed to complete the EyeSimplify VF in a quiet, dark room free of distractions. The research assistant will be available via email or telephone to troubleshoot any issues that may arise.
- The EyeSimplify uses a 24-2 examination protocol with a Neighborhood-Zippy Estimation by Sequential Testing (ZEST) testing algorithm. Background brightness will be set to 15.8 ASB. The test will use a scaled white stimulus. Subjects will self-administer the EyeSimplify VF at home. The EyeSimplify VF will be deemed unreliable if FP >15%. The HFA uses a 24-2 examination protocol with a SITA standard testing algorithm. A clinical technician will administer the HFA VF at the University of Iowa Hospitals and Clinics' Glaucoma clinic. The HFA VF will be deemed unreliable if FP >15%. At the conclusion of the study, subjects will complete a satisfaction survey regarding testing using the EyeSimplify VF.
- VII.E.7** *Will you attempt to recontact subjects who are lost to follow-up?*
Yes
- VII.E.8** *Describe - any procedures need to be included in the consent:*

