- Electronic records (computer files, electronic databases, etc.) - All electronic files will be kept as files on an encrypted, password-protected UIHC Department of Ophthalmology network server. There will be no identifiers or link available on any transferred data; therefore, there will be no way to compromise patients' privacy or confidentiality.
 - Name - [name]
 - Title - Senior IT Support Consultant
 - University Job Classification - Faculty/Staff
- Paper/hard copy records (hard copy surveys, questionnaires, case report forms, pictures, etc.) - Informed consent documents will be transported directly from the UIHC Glaucoma clinic to a locked file cabinet in the PI's office within the Department of Ophthalmology and Visual Sciences immediately following the study recruitment clinical encounter by the PI or research assistant. These documents will remain in this locked cabinet for the duration of the study.

X.5 Do the confidentiality protections indicated above allow only members of the research team to access the data/specimens?

No

X.6 Describe

M&S Technologies, the developers of the EyeSimplify web-based visual field test, maintain a secure, encrypted, HIPAA-compliant database of patient testing information. This database includes study ID (de-identified), birth year, and experimental visual field testing data. M&S Technologies does not have access to any additional patient information.

X.7 Does your study meet the NIH criteria for a [Certificate of Confidentiality](#) or will you be applying for Certificate of Confidentiality?

No

XI. Data Analysis

XI.1 Describe the analysis methods you will use, including, if applicable, the variables you will analyze

Variables: Clinical data including age, gender, ethnicity, Humphry Visual Field performance, EyeSimplify Visual Field performance, and satisfaction survey will be collected and analyzed.

Data analysis: Humphrey Visual Field Guided Progression Analysis (GPA) and EyeSimplify Visual Field mean deviation linear trending will be compared using Bland-Altman analysis.

XI.2 Provide the rationale or power analysis to support the number of subjects proposed to complete this study.

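### XI.1 applies Bland-Altman to an HFA progression analysis and an EyeSimplify mean deviation trend without a common quantity, unit or time window

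*Combined protocol and SAP*

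**What the plan says.** Section XI.1 (Data Analysis) names one statistical method: "Humphrey Visual Field Guided Progression Analysis (GPA) and EyeSimplify Visual Field mean deviation linear trending will be compared using Bland-Altman analysis". The sentence before it lists variables, ending with "Humphry Visual Field performance, EyeSimplify Visual Field performance, and satisfaction survey will be collected and analyzed", and gives no method for any of them.

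The comparison serves Aim 2 in I.5: "Determine the concordance of EyeSimplify to the Humphrey Visual Field Analyzer (Carl Zeiss Meditec Inc., Dublin, CA) in identifying visual field loss progression". It is also the only method that could bear on the secondary hypothesis, that EyeSimplify will be "non-inferior to the Humphrey Visual Field Analyzer in identifying glaucomatous progression trends". No margin is given for that hypothesis.

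Three other places bear on what can be compared:
- I.4 allows retrospective record review alongside prospective testing.
- I.6 puts typical HFA testing at intervals of 6 to 12 months.
- VII.E.6 has HFA fields taken as part of routine care, and EyeSimplify tests at home biweekly for six months.

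No section defines GPA, names the GPA output to be used, or gives its unit or period.

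**The concern.** Bland-Altman takes x minus y for each pair, reports the mean difference as bias, and sets limits at 1.96 SD of the differences around it. That is informative only if x and y measure the same thing on the same scale. XI.1 puts a progression analysis on one side and a linear trend of a named index on the other. An analyst following the text would have to invent a definition of the HFA value before subtracting anything, and different choices would give different biases and limits.

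At stake is the evidence on progression. If the scales differ, the bias and limits reflect the units. If the scales match but the periods differ, the limits mix device disagreement, real change between periods, and slope noise. In neither case could the result be read as agreement or disagreement in identifying progression.

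**Working it through.** The plan gives no figure to reproduce here: it states no agreement limit, SD or margin for this comparison. The check therefore has three steps.

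**1. The two sides as the documents describe them**

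| | HFA | EyeSimplify |
|---|---|---|
| Value entered (XI.1) | GPA, output not named | MD linear trend |
| Unit | not stated | not stated; dB per unit time follows from a linear trend in MD |
| Period | not stated; earlier records allowed (I.4) | six study months (VII.E.6) |
| Frequency | routine, typically every 6-12 months (I.6, VII.E.6) | biweekly (VII.E.6) |

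No row is matched between the two columns.

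**2. What a scale mismatch does under perfect concordance**

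This step is an illustration. Assume true MD slopes with mean -0.5 and SD 0.5 dB/year, and let the HFA value be k times the slope. The difference is then (k - 1) × slope.
- k = 1: bias 0, limits 0 to 0.
- k = 2: bias -0.50, limits -0.50 ± 1.96 × 0.5 = -1.48 to 0.48.
- k = 3: bias -1.00, limits -2.96 to 0.96.
- A 0/1 progression flag (slope below -0.5) minus the slope: apparent bias 1.00, limits -0.85 to 2.86.

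The devices agree perfectly in every case, so these values come from the units alone.

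**3. The charitable reading: GPA taken as an MD rate in dB/year**

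With fields 6 to 12 months apart, a six-month window holds at most two fields (one at each end) and possibly none. An HFA rate must then use earlier records, or rest on about two points.

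The slope SE is s/√Sxx, where s is the test-to-test SD of MD. Assume a straight line, independent errors and the same s for both devices. Per 1 dB of s:
- EyeSimplify, 13 tests two weeks apart: Sxx = (2/52)² × 182 = 0.2692, so SE = 1/0.519 = 1.93 dB/year.
- HFA, two fields 0.5 year apart: SE = √2/0.5 = 2.83 dB/year.
- HFA, seven six-monthly fields over three years (an assumed history): Sxx = 0.25 × 28 = 7, so SE = 0.378 dB/year.

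Limits from noise alone are ±1.96 × s × √(SE₁² + SE₂²):

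| HFA series | s = 1.0 dB | s = 1.5 dB |
|---|---|---|
| Three-year history | 1.96 × √(1.93² + 0.378²) = ±3.8 | ±5.8 |
| Two fields, six months apart | 1.96 × √(1.93² + 2.83²) = ±6.7 | ±10.1 |

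If biweekly is read as twice a week (about 52 tests), the EyeSimplify SE falls to 0.96. At s = 1.0 the limits become 1.96 × √(0.96² + 0.378²) = ±2.0 against the three-year history.

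Step 3 measures slope noise under matched units. It does not measure the size of the unit mismatch in step 2.

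**The case against.** The strongest reply is that GPA is undefined in the documents. They do not say it is a category, a rate on another index, or non-numeric, and the secondary hypothesis speaks of trends, which fits a trend-to-trend comparison. If the HFA value were an MD slope, Bland-Altman would be a valid agreement method. This stands. A reader might infer that the analysis has no meaning under any reading, but that needs knowledge of GPA from outside the documents. What the documents support is that no common quantity, unit or window is set.

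A reader might also infer that XI.1 contains the only planned analysis. It contains the only named statistical method. Other variables are also to be analysed, compliance and tolerance are to be assessed from test records and a survey (I.5), and VII.E.6 has a per-test rule, "The EyeSimplify VF will be deemed unreliable if FP >15"%. The primary hypothesis, "Primary Hypothesis: The EyeSimplify visual field test will produce reliable visual field testing data", concerns reliability and is not touched by this point.

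A third reply is that wide limits are imprecise, which is different from uninterpretable. This also stands for step 3. With 50 pairs, the 95% interval for the mean bias would be the limits divided by √50: about ±0.5 to ±0.8 dB/year against the three-year history, and ±0.9 to ±1.4 against two fields. That narrower interval still does not say what the bias means when the two rates come from different periods.

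Finally, the test SD has no source in the documents, and no section fixes the HFA window as past or concurrent. Both are treated as open here.

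**Conclusion.** The point holds as a fault in the stated method. XI.1 subtracts two values that the plan never puts on the same quantity, unit or window, so the bias and limits as written are not interpretable for Aim 2 or the secondary hypothesis.

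Reading GPA as an MD rate does not rescue the comparison. The routine HFA schedule leaves about 0-2 fields in the six study months, so the rates would cover different periods or the HFA rate would rest on about two points. Noise alone would then give limits of roughly ±3.8 to ±10.1 dB/year. That range is illustrative: it rests on an assumed SD of 1.0-1.5 dB in both devices, 13 two-weekly tests with none missed, and the two assumed HFA series.

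A reader might infer that the result is lost for all 50 subjects. Fifty is the enrolment target in VI.1. The documents do not give the number who would enter this comparison, so no count of affected subjects can be stated.

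**What to change.** Replace the sentence in XI.1 with two separate comparisons.

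- **Measurement agreement.** Apply Bland-Altman to MD in dB from both devices, same eye, pairing each available routine HFA field with the nearest EyeSimplify test or tests. State the maximum gap allowed within a pair, and allow for repeated pairs or two eyes from one subject.
- **Progression, descriptively.** Either report MD slopes in dB/year from both devices, with each device's window stated and slope uncertainty shown, or, if GPA is used as a category, cross-tabulate it against an EyeSimplify progression rule fixed in advance. Do not enter GPA output into Bland-Altman.

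With one pair per subject, each limit of agreement would have a 95% half-width of 1.96 × √(1/n + 1.96²/(2(n - 1))) SDs of the differences. That is 0.48 SD at n = 50, and 0.74 SD at n = 21 if the analysed fraction matched the study cited in XI.2 (50 × 20/47 = 21).

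The cost is a paragraph of text and a re-analysis, with no new tests. Home testing starts within a week of consent (VII.D.28), and consent takes place at a scheduled clinic appointment (VII.D.29), so an early pair is possible wherever a routine HFA field was taken around that visit. No section guarantees one, and only eyes with an HFA field near a home test contribute. Paired MD shows measurement agreement and does not by itself answer the progression question, so the Aim 2 conclusion on progression becomes descriptive. The closure notice is dated 09/05/25, so the change belongs in the reported analysis, disclosed as a departure from XI.1.
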